10. STUDY ENDPOINTS*

Primary Outcomes Measures:

1. To assess the effect of OA Careplan on (a) decision quality using a validated Decisional Conflict Scale and (b) pre-to-post decision pain relief and functional gain, using the HOOS (for hip patients) or KOOS (for knee patients).
2. To evaluate the effect of the OA Careplan+Support on (a) decision quality using Decisional Conflict Scale and (b) pre-to-post decision pain relief and functional gain, using the HOOS or KOOS.

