12. DATA AND SPECIMEN BANKING*

No specimens will be banked for future use. See #13, Data Management, for data retention and access.

13. Data Analysis and Management*

Responsibility for 6 month and 12 month outcome data collection was transferred from UMMS to Northwestern during 2021. At the completion of study enrollment (on or about March 1, 2022), the UMMS data enrollment and collection services will be completed. At that date, the UMMS data center will have already, or will then, transfer all enrollment, patient-reported, and study data to Northwestern for the analytic team to manage and analyze. The UMMS data center will confirm that they expunged all ASK study data from the web-based data capture systems (DatStat, RedCap) and UMMS data storage files within UMMS.

Aim 1

We will transcribe recorded interviews and code using content analysis techniques to identify themes. We expect to achieve data saturation at or before completing 30 interviews with patients and 30 with caregivers.

AIM 2 and 3. Sample size and effect size estimates:

The trial is designed with $\geq 80\%$ statistical power at 5% significance level to detect intervention effects that are meaningful to both patients and surgeons, and health systems. In total, 40 (Aim 2) or 54 (Aim 3) surgeons will be randomized equally to treatment and control arms with an average of 100 patients/surgeon. Based on data from FORCE-TJR, the intraclass correlation within surgeon is approximately 0.02. Using two independent group t-tests adjusting for within surgeon clustering, the trial can detect an intervention effect of (a) improved decision quality of >0.16 SD ; (b) improved quality of OA care defined in two ways: 6 month post-decision pain relief (KOOS/HOOS) of ≥ 3.3 points for TKR patients (34.1 vs. 37.4; SD=20.8) and ≥ 3.3 for THR patients (45.7 vs. 49.0; SD=20.9) or greater proportion of patients with meaningful pain relief (17 points in HOOS/KOOS pain score) of $\geq 6.1\%$ more TKR patients (77.9% vs. 84.0%) and $\geq 4.2\%$ more THR patients (90% vs. 94.2%).

Aims 2 and 3: Overview of analytic approach. We hypothesize (Aim 2) that patient/clinician use of the OA Careplan will improve decision quality as well as

INVESTIGATOR STUDY PLAN

12.14.2021

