satisfaction with the OA care decision, as compared to usual care. Further, we hypothesize that improved decision quality will mediate quality of OA care as measured by lower pain and higher function at 6 and 12 months (KOOS/HOOS) after decision for both TJR and non-operative care. In Aim 3, we hypothesize that the OA Careplan+Support (vs. OA Careplan alone) will incrementally enhance decision quality and quality of OA care (for those who choose to use the Support) with the same measures used in Aim 2.

The general analytic approaches for Aims 2 and 3 are similar and summarized here. The underlying models extend our previous award-winning TKR outcome prediction model where discrete outcome sub-groups were identified. We will adhere to the intent-to-treat principle to analyze the trial data; the intervention status of the surgeon/site and their patients will be analyzed according to their status at the time of intervention. First, descriptive statistics for all relevant outcomes will be tabulated by treatment arm. Select patient factors (e.g., race, sex, function; comorbid factors) that may contribute to heterogeneity of treatment effects will be compared using univariate methods such as t-test for normally distributed variables, Wilcoxon rank sum test for skewed continuous variables, or Chi² test for categorical variables. We will examine distributions of outcomes, identify proper distribution assumptions, and determine whether or what types of transformations are indicated.

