will be entered into the same model in order to assess their contributions to the outcome under analysis, after adjusting for each other, as well as the patient-level covariates. Model assumptions will be carefully examined. In these model-building processes, effect modifications will be examined by including interaction terms between relevant covariates, and to ensure the heterogeneity of the intervention effects among patient subgroups are adequately considered. The analyses will be conducted with all patients; and then for TKR and THR patients separately. While the primary goal is to understand patient-level covariates with outcomes, it is critical to assess surgeon/site factors that may influence outcome for all, or sub-groups of patients. For example, obese, diabetic patients with cardiac disease may have more positive decision quality and pain relief with a more experienced high-volume surgeon.

Aim 2: To assess the effect of OA Careplan on (a) decision quality and (b) pre-to- post decision pain relief and functional gain, we will do the following. We expect 20 surgeons and 2000 patients will receive the OA Careplan intervention, and another 20 surgeons and 2000 patients will receive usual care. The analyses will be conducted with all patients; and then for TKR and THR patients separately. First, we will tabulate the decision quality and care outcomes by arm and for select patient subgroups (e.g., sex, age, race/ethnicity). Second, we will use GLLAMM to estimate adjusted Careplan intervention effects by including in the models a Careplan indicator (Careplan intervention=1 vs. usual care=0) and a set of site/surgeon and patient variables for adjustment. A statistically significant coefficient of the Careplan indicator signals possible intervention effect. In this analysis, interaction terms between the Careplan indicator and surgeon or patient factors will be examined, statistically significant interaction terms may suggest the existence of heterogeneity in intervention effects. If present, intervention effects will be analyzed and presented by subgroups.

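### Arm contrasts within TKR and THR patients, read literally, condition on a surgery choice made after randomisation; the by-joint split should use the baseline knee or hip instead

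*Combined protocol and SAP*

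**What the plan says.** Section 13 gives the order of the intervention analyses twice, in the overview for Aims 2 and 3 and in the Aim 2 paragraph: "The analyses will be conducted with all patients; and then for TKR and THR patients separately". The Aim 2 paragraph then estimates covariate-adjusted Careplan effects.

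The sample-size paragraph of the same section states its detectable pain effects by procedure only. It gives 3.3 "points for TKR patients (34.1 vs. 37.4; SD=20.8"), the same difference for THR patients (45.7 vs 49.0; SD 20.9), and responder proportions of 77.9% vs 84.0% (TKR) and 90% vs 94.2% (THR). It gives no pain figure for all patients together.

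Other sections bear on the meaning:

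- Section 4 delivers the Careplan at the consultation to help patients decide between joint replacement and non-operative care, with tailored estimates of surgical benefit and risk.
- Section 5 describes surgery as a joint decision of patient and surgeon at that evaluation.
- Section 10 defines the pain and function endpoints by joint, "using the HOOS (for hip patients) or KOOS (for knee patients"), with no restriction to operated patients.
- Section 13 commits to intent-to-treat: "We will adhere to the intent-to-treat principle to analyze the trial data". Its hypothesis covers both surgical and non-operative patients.
- For Aim 3, Section 13 recognises that use of the Support is not randomised and plans inverse propensity weighting. It has no such provision for the choice of surgery.

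**The concern.** Patients are enrolled while surgery is still undecided, and the intervention supplies information bearing on that decision. If it shifts who has surgery, the TKR patients in the Careplan arm and those in the usual-care arm are no longer alike at baseline. A difference in mean pain relief between them then mixes any effect on outcome with a change in who is in the group. If patients with poor expected gain leave surgery in the Careplan arm, the contrast looks favourable. If such patients are drawn into surgery, it looks unfavourable.

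The by-procedure results are the ones for which the plan states meaningful pain effects, and nothing labels them as descriptive. Under the literal reading, non-operative patients also appear in no by-joint result.

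**Working it through.** **Inputs from the sample-size paragraph of Section 13.** "statistical power at 5% significance level to detect intervention effects" (power at least 80%; two-sided testing is assumed because sidedness is not stated); 40 surgeons in Aim 2, where "surgeons will be randomized equally to treatment and control arms with an average of 100 patients/surgeon"; "the intraclass correlation within surgeon is approximately 0.02"; "Using two independent group t-tests adjusting for within surgeon clustering"; difference 3.3, SD 20.8 (TKR) or 20.9 (THR).

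**Step 1: reproduce the plan's figure.**

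- Design effect = 1 + (100 - 1) x 0.02 = 2.98. Effective n per arm = 20 x 100 / 2.98 = 671.
- Standard error (TKR) = 20.8 x sqrt(2/671) = 1.135. Then 3.3/1.135 = 2.91, and 2.91 - 1.96 = 0.95, so power is 82.8%. For THR it is 82.4%.
- Detectable difference at 80% power = 3.18 points with normal quantiles, or 3.27 with t quantiles on 38 df (THR 3.20 and 3.28). The t version rounds to the stated 3.3.
- The responder proportions give 81.3% (TKR) and 81.5% (THR).

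The figures reproduce, but only if the full 100 patients per surgeon are used for TKR and again for THR.

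**Step 2: selection with no effect on any patient.** Suppose the Careplan arm moves the fraction f of TKR candidates with the lowest predicted gain to non-operative care, changes nobody's pain result, and predicted gain explains a share R² of variance. The mean gain of those remaining rises by

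shift = [phi(z_f) / (1 - f)] x sqrt(R²) x SD.

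For f = 0.10 the bracket is 0.1755/0.90 = 0.195. For f = 0.20 it is 0.280/0.80 = 0.350. With SD 20.8:

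| f | R² = 0.10 | R² = 0.20 | R² = 0.30 |
|---|---|---|---|
| 0.10 | 1.28 | 1.81 | 2.22 |
| 0.20 | 2.30 | 3.26 | 3.99 |

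f and R² are assumptions; the documents give neither. THR values are almost the same (SD 20.9).

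**Step 3: effect on the test.** A simulation of 2,000 trials used 40 surgeons with 100 patients each and ICC 0.02. It assumed that half choose surgery and that moved patients have the same gain either way. Surgeon means were compared by t-test without covariates. r is the assumed correlation of predicted with actual gain (r = 0.3 and 0.5 are R² = 0.09 and 0.25).

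| Moved | r | Operated-only difference | False finding of benefit |
|---|---|---|---|
| none | 0.5 | 0.0 | 2.4% |
| 10% | 0.3 | 1.2 | 14% |
| 10% | 0.5 | 2.0 | 31% |
| 20% | 0.3 | 2.1 | 34% |
| 20% | 0.5 | 3.6 | 75% |

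The all-patient difference stayed at 0.0 in every row, with false benefit in 2-3% of trials.

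**Step 4: covariate adjustment.** Section 13 plans adjusted models, so Step 2 was repeated with linear adjustment for a covariate carrying part of predicted gain. If it carries all of it, the bias is about 0. If it carries 75% of its variance, the bias is 0.4-1.2 points across the six cells. If it carries 50%, it is about 0.6-2.2 points.

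**The case against.** Five points on the other side deserve weight.

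- **The randomised comparison survives.** In both places the all-patient analysis comes first, and the Section 10 endpoints are not limited to operated patients. A reader might infer that the trial's main pain conclusion is compromised. The documents do not support that: the problem is confined to the follow-on contrasts.
- **Intent-to-treat is not breached.** A reader might see a contradiction with that commitment. Section 13 applies it to the intervention status of surgeons, sites and patients, and subgrouping leaves that status unchanged. Forming a subgroup after randomisation is a separate problem.
- **TKR and THR may be shorthand for knee and hip.** No non-operative stratum is listed, and the power figures allow 100 patients per surgeon to each procedure, so they cannot describe the operated groups the trial would actually have. Against this, Section 10 speaks of hip and knee patients when it means the joint, and no text defines TKR or THR otherwise. The ambiguity stands, and the same edit resolves it.
- **Adjustment would shrink the bias.** The candidate covariates (pain severity, function, comorbidity) overlap with what the Careplan displays, and none of the adjusted figures in Step 4 reaches 3.3. But the covariates are only candidates screened at p < 0.10, and patient goals, which the Careplan shows, are not among them. Adjustment does not restore randomisation.
- **The inputs are assumed and run one way.** Even unadjusted, about 3.3 points needs 20% moved and R² of at least 0.20. Section 5 ties pre-operative factors to functional gain and does not show that pain relief is predictable. The Careplan is described as guiding decisions, which could also bring patients into surgery.

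**Conclusion.** The concern holds for the TKR-only and THR-only contrasts under the literal reading. They condition on a choice made after randomisation that the intervention may influence, and the plan gives no estimand, method or caveat for this. They could show a pain difference in either direction with no patient's outcome changed.

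The size is unknown. The unadjusted 1.3-4.0 points rest on assumed diversion of 10-20%, assumed R² of 0.10-0.30, and selection in one direction. They show that a bias comparable with the stated 3.3 points is possible, not that it is expected; adjustment would reduce it by an amount the documents do not allow one to state. A reader might conclude that the Careplan will produce a false benefit. Without a surgery rate by arm or a measure of predictive strength, the documents do not support that.

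The all-patient contrast can carry the conclusion on quality of OA care.

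**What to change.** 1. In both places in Section 13, replace the split into TKR and THR patients with a split by baseline index joint, knee or hip, whatever treatment is chosen.
2. Add a rule fixing the index joint from the baseline survey. Section 8 lets patients report more than one joint of concern.
3. State that the all-patient contrast carries the conclusion on quality of OA care.
4. Report surgery rate by arm, so that a reader can see whether the operated groups were formed differently.
5. Label any operated-only or non-operative-only comparison as non-randomised and descriptive.
6. In the sample-size paragraph, state that the TKR and THR detectable effects describe operated patients and not the knee and hip strata.

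No new data collection is needed, since knee and hip baseline surveys already exist. The costs are the index-joint rule and by-joint estimates that include non-operative patients and so may be more variable. The plan gives no mean or SD for such strata, so they would have no stated detectable effect until one is derived.

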Because the trial data are hierarchical in nature (repeated measures of the same patient nested within participating surgeons/sites), we will use hierarchical generalized linear latent and mixed models (GLLAMM) to analyze the trial data. The model will consider information at the patient and surgeon levels. The basic unit of analysis is at the patient level. Patients nested within the surgeon/site will be considered exchangeable, and sites/surgeons are considered independent from each other. To account for potential imbalance in site/surgeon and patient characteristics, we will adjust for surgeon/site and patient factors in the regression models. Candidate patient level covariates include joint pain severity, pre-decision physical function level, and comorbid conditions, such as diabetes, renal disease, pulmonary disease, depression, obesity, or congestive health failure. Candidate surgeon variables for adjustment include annual surgical volume, procedure type, or geographic region of US. We will follow the parsimonious principle to derive the final models for evaluating intervention effects. First, we will use GLLAMM models to analyze the association of each plausible patient-and site/surgeon-level factor with the outcomes (quality of decision, change in pain severity, function). Those statistically significant variables ($p < 0.10$) will be included in a subsequent analysis using multivariable models to identify a parsimonious set of independent patient-and site/surgeon-level covariates. Model development will be guided by clinicians and patient advisors to assure that clinically important variables are included. To identify independent site/surgeon-level variables, we will include each of the significant variables separately while forcing the patient-level covariates into the models. The significance of each site/surgeon-level variable will be determined using (partial) likelihood ratio tests. We will identify a subset of site/surgeon indicators that contribute to outcomes ($p < 0.10$), independent of individual-level factors. Furthermore, this subset of significant indicators

INVESTIGATOR STUDY PLAN

12.14.2021

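### Aim 2 subgroup effects are triggered by a significant interaction over an open set of factors, with no interaction alpha, no multiplicity control and no statement that the overall effect stays the main result

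*Combined protocol and SAP*

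**What the plan says.** The rule is in the Aim 2 paragraph of Section 13 (Data Analysis and Management). An adjusted arm effect is estimated from a mixed model with a 0/1 Careplan indicator and adjustment variables, and a significant coefficient on that indicator is read as a sign of a possible effect. Within this analysis, "interaction terms between the Careplan indicator and surgeon or patient factors will be examined", and "statistically significant interaction terms may suggest the existence of heterogeneity in intervention effects". The consequence follows at once: "If present, intervention effects will be analyzed and presented by subgroups".

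No list of modifiers is attached to that rule. Section 13 names factors in three other places:

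- The overview of the analytic approach, for adjustment: "Candidate patient level covariates include joint pain severity, pre-decision physical function level, and comorbid conditions, such as diabetes, renal disease, pulmonary disease, depression, obesity" (the sentence goes on to heart failure), and "Candidate surgeon variables for adjustment include annual surgical volume, procedure type, or geographic region of US".
- The Aim 2 paragraph, as examples of subgroups to tabulate: sex, age and race/ethnicity.
- The overview again, as examples of patient factors through which the effect might differ: race, sex, function and comorbidity.

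Two significance levels appear. The sample size paragraph claims at least 80% "statistical power at 5% significance level to detect intervention effects". The overview uses p < 0.10 to screen covariates, and those that pass "will be included in a subsequent analysis using multivariable models to identify a parsimonious set". Neither level is assigned to the interaction tests.

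**The concern.** Reporting that depends on a significant interaction, over a set of factors that is not closed, will often produce subgroup effects by chance. The plan gives a reader no means of telling a chance pattern from a real one: the factors are not fixed, the level is not stated, and the number of tests is not allowed for. In a decision-support trial, a false claim that the Careplan helps one group and not another could steer who is offered it.

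There is a second, conditional issue. Success is read from the Careplan coefficient, and effect modification is examined within the same model-building. The plan does not say that the coefficient comes from a model without interaction terms. If an interaction with an uncentred factor were kept, the coefficient would describe the reference subgroup and not the average difference between the randomised arms.

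**Working it through.** **1. The plan's own figures.** No error rate is given for the interaction tests, so there is none to reproduce. The figures that exist concern the arm contrast, and the one for decision quality reproduces. With 100 patients per surgeon, an intraclass correlation of 0.02 and 2,000 patients per arm, the design effect is 1 + (100 − 1) × 0.02 = 2.98 and the effective size is 2000 / 2.98 = 671 per arm. The detectable difference at 80% power and two-sided 5% is (1.960 + 0.842) × √(2 / 671) = 0.153 SD, or 0.157 SD using a t distribution with 38 degrees of freedom. The plan states 0.16 SD. This calculation covers the arm contrast; it includes no interaction test.

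**2. Number of factors (an inference, not a stated list).**

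- For adjustment, patient level: pain, function, diabetes, renal disease, pulmonary disease, depression, obesity, heart failure = 8.
- For adjustment, surgeon level: volume, procedure type, region = 3.
- As tabulation examples: sex, age, race/ethnicity = 3.
- Total: 8 + 3 + 3 = 14.
- Narrower count, from the overview's remark on differing effects: race, sex, function, plus the six named comorbidities = 9.

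**3. Chance of at least one false interaction for one outcome.** With k independent tests at level α and no true heterogeneity, this is 1 − (1 − α)^k. Taking α = 0.05 as an assumption:

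| k | Calculation | Result |
|---|---|---|
| 3 | 1 − 0.95^3 | 14% |
| 8 | 1 − 0.95^8 | 34% |
| 9 | 1 − 0.95^9 | 37% |
| 11 | 1 − 0.95^11 | 43% |
| 14 | 1 − 0.95^14 | 51% |

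If the covariate-screening level of 0.10 were used instead, 14 tests would give 1 − 0.90^14 = 77%.

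**4. Allowing for correlation within an outcome.** Simulating 14 test statistics with a common correlation (400,000 draws, α = 0.05):

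| Correlation | At least one false interaction |
|---|---|
| 0 | 51% |
| 0.1 | 50% |
| 0.2 | 47% |
| 0.3 | 44% |
| 0.5 | 35% |

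**5. Several outcomes.** The overview screens factors against three outcomes: decision quality, change in pain, and function. That makes 14 × 3 = 42 tests, with 42 × 0.05 = 2.1 false interactions expected. The chance of at least one is 1 − 0.95^42 = 88% if all are independent. It is 83% by simulation if statistics correlate 0.6 across outcomes and are independent within an outcome.

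**6. Effect of adjustment.** Testing each of 14 factors at 0.05 / 14 gives 1 − (1 − 0.05/14)^14 = 4.9%.

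**7. Meaning of the coefficient.** With arm A (0/1) and factor X, write the mean outcome as b0 + b1·A + b2·X + b3·A·X. The average arm effect is b1 + b3 × mean(X). It equals b1 only if b3 = 0 or X is centred; otherwise b1 is the effect at X = 0. As an invented illustration with real heterogeneity, take effects of +5 in 80% of patients and −3.5 in 20%. The average is 0.8 × 5 + 0.2 × (−3.5) = 3.3, while b1 reads 5 if the larger group is the reference.

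**The case against.** A reader might infer that false subgroup effects would replace the overall arm effect. The text does not support that. The Aim 2 paragraph plans analyses in all patients before knee and hip separately, and the adjusted arm effect comes before interactions are examined. The subgroup sentence adds results and removes none. The Aim 3 text plans effects both overall and by subgroup. This part of the objection stands in full.

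It is also fair to say that 14 is not the plan's number. Eleven of the factors are candidates for adjustment, to be thinned by screening, and three are examples for tabulation. The 5% level is borrowed from the power statement. Both points stand, so every percentage above is conditional. They do not remove the gap, because the plan's lists are given as examples and the number tested could be smaller or larger than 14.

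A reader might extend the trigger to Aim 3. The conditional rule is written only for Aim 2; the shared overview says only that effect modification will be examined.

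Finally, the plan does not say that an interaction is retained in the model from which the Careplan coefficient is read, and centring would avoid the problem. That is right, so the coefficient issue is a possibility the wording leaves open, not an error it commits. Planning an analysis in all patients does not close it: that phrase contrasts pooled with joint-specific analyses and does not describe the model's terms.

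The cautious wording, that significant interactions may suggest heterogeneity, helps interpretation but does not change the reporting rule.

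**Conclusion.** The point holds as a gap in pre-specification. For Aim 2, subgroup presentation follows from a significant interaction over an open set of factors. There is no stated level, no control for the number of tests, and no statement that the overall effect remains the main result.

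The chance of at least one false subgroup finding per outcome is about 35% to 50% under three assumptions: 14 factors are tested, each at 5%, with test statistics correlated between 0.1 and 0.5. It is 51% under independence and 37% for nine independent factors, and it rises over several outcomes. All these figures assume no true heterogeneity.

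The documents do not support the conclusion that the randomised comparison would be lost. Whether the tested Careplan coefficient could become a reference-subgroup effect depends on a modelling choice that the plan leaves unstated.

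**What to change.** Amend the Aim 2 text of Section 13 as follows:

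- State that, for each outcome, the arm effect from the model without interaction terms is the main result, whatever the interaction tests show.
- Fix a short list of baseline modifiers before the arms are compared. It could be drawn from those the overview already mentions: race, sex, function and comorbidity.
- Report each listed interaction with its confidence interval whether or not it is significant, and state the alpha or an adjustment such as Holm within each outcome.
- Label every other interaction exploratory.

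The change is to wording only and needs no new data. The plan is dated December 14, 2021, and Section 9 places completion of the primary analyses in 2022. If Aim 2 outcomes have already been examined by arm, the amendment should say so. The downside is that fewer subgroup claims can be made.
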